3.2 Primary endpoints

- Predict neurocognitive decline based on RT dosimetric and other explanatory variables like gender, age at diagnosis, comorbidities, level of education, social factors such as social activity and occupation, tumour size and localization, pathological/genetic/molecular characteristics, therapy protocols (surgery, radiotherapy and/or chemotherapy) in an NTCP model for each cognitive domain
- Measure the prevalence and severity of neurocognitive decline compared to baseline at one year, for all cognitive domains (attention, memory, working memory, information/visuomotor processing speed, executive functioning)

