7.1 Sample size

Study subjects will be recruited from the radiation-oncology center of three centers: UZ Leuven, UZ Gent and Iridium Kankernetwerk Antwerpen. From a pragmatic perspective, we estimate to recruit 12-15 patients yearly in each of the three centers, resulting in 120 patients in three years in total.

Cognitive impairment has been reported in primary brain tumour patients and is roughly estimated to be present in about half of patients³⁹⁻⁴⁰. Although limited (good quality) evidence exists for our

type of study, power calculations were performed based on the two most extreme studies (i.e. one showing minimal amount of cognitive impairment⁴¹ and one showing maximal amount of cognitive impairment⁴². In both studies cognitive performance is assessed at baseline and about 12 months after radiotherapy in primary brain tumours. In the study by Moretti et al⁴², we used the cognitive outcome results of patients 9-12 months after radiotherapy (45-60 Gy), since the studied population will receive radiotherapy doses within this range. For power calculations, we used the performance on the digit span forward (processing speed) since the prevalence of impairment on this test was low (<20%). Based on these studies, effect sizes of d= 0,368 and d= 1,271 were found with a power of 0,800 and 0,868 respectively. This power would be 0,979 and 1,000 in our specific explorative study, in case of 120 inclusions. In order to detect this difference after 12 months with a power of 0.800 and a two-sided significance level α =0,05, the total required sample size would thus range between 8-60 patients. Power calculations were performed using Gpower 3.1⁴³.

Sample size calculation for the prediction models was performed using a recently developed software package⁴⁴. Since the event rate of cognitive impairment is unclear, we performed power calculations for the lowest and highest event rate, i.e. 0,2-0,5 (see above). When considering 4 candidate predictors and rMSPE of 0,1, the required sample sizes ranges between 90 and 120 patients respectively. Therefore, including 120 patients will allow building a sufficiently complex prediction model combining four dosimetric and/or clinical features.

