7.2.1 Neuropsychological data

The following research questions are addressed by using multiple statistical tests.

- 1. How severe is the neurocognitive decline after treatment and how does it change over time?
- 2. Which neurocognitive domains are affected in which patients?

The first question is addressed by investigating the neurocognitive performance of primary brain and base of skull tumour patients. The performance on neurocognitive measures of the patients will be assessed at 3 timepoints over time. The raw test-scores are converted to normalized zscores based on normative data for each cognitive test. For each cognitive test, cognitive impairment is defined as a z-score \leq 1.5, and patients will be dichotomized according to their impairment status (impaired versus unimpaired). The frequency of impairment will be reported as descriptive information.

We will assess the evolution in the z-scores with a mixed repeated measures model to test changes throughout time. However, if the data are not normally distributed, the Friedman test will be used as alternative approach. The effects of the patient- and treatment-related predictors on the neuropsychological and questionnaire scores will be investigated using general linear models (predictors= tumour location, radiation dose, covariates= gender, age at treatment, time since treatment and socio-economic status) at each timepoint. Bonferroni correction will be applied as

method for statistical correction of multiple tests, for each test outcome (n=5 outcomes; memory, executive functioning, attention, visuomotor function, working memory) that is predicted.

Effect sizes of the tests will be reported. Partial eta squared (hp2) will be computed to estimate effect sizes (weak effect: $np^2 \approx 0.03$; moderate: $np^2 \approx 0.06$; large: $np^2 \geq 0.14$) for linear relationships between predictor and each outcome (e.g. age, time since treatment). Cohen's d will be used to estimate effect sizes for subgroup differences (small effect: 0.2 < d < 0.3; medium: 0.3 < d < 0.8; large: d > 0.8).

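### The one-year decline endpoint has no one-year test: Section 7.2.1 names only a three-visit test of change, with a fallback that cannot isolate one year

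*Protocol*

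**What the plan says.** Protocol Section 3.2 lists two primary endpoints. One is the NTCP prediction model. The other is "Measure the prevalence and severity of neurocognitive decline compared to baseline at one year, for all cognitive domains".

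Section 7.1 gives a power calculation on the same time frame. It takes effect sizes from two published studies: "In both studies cognitive performance is assessed at baseline and about 12 months after radiotherapy in primary brain tumours". It reports that "effect sizes of d= 0,368 and d= 1,271 were found with a power of 0,800 and 0,868 respectively" and adds: "This power would be 0,979 and 1,000 in our specific explorative study, in case of 120 inclusions". The required number of 8 to 60 patients is the number needed "In order to detect this difference after 12 months with a power of 0.800", at a "two-sided significance level α =0,05".

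Sections 5.1 and 5.2 schedule cognitive testing at baseline, 1 year and 2 years. For the analysis, Section 7.2.1 says: "We will assess the evolution in the z-scores with a mixed repeated measures model to test changes throughout time". If the data are not normally distributed, the Friedman test takes its place. The frequency of impairment is reported descriptively. The general linear models in the same section examine predictor effects at each timepoint, not change from baseline. Section 7.2.1 names no baseline-to-1-year comparison and does not limit the analysis of this endpoint to the first two visits.

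**The concern.** The endpoint and the power statement concern two visits, and the test concerns three. An overall test over three visits asks whether the means differ anywhere among baseline, 1 year and 2 years. It can be significant because of a change that appears only at 2 years, and then it says nothing about one year. Section 4.3 itself describes neurocognitive decline as progressive, so change after the first year is a realistic possibility.

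The mixed model could still answer the one-year question if the right contrast is read from it. The Friedman test over three visits is an overall rank test by construction and has no one-year component. Under the protocol's own fallback, the one-year question would have no inferential answer. A reader could also attach the power of 0.979 to a test for which it was not calculated.

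**Working it through.** **Step 1: identify the test behind the stated power.** Inputs from Section 7.1: d = 0.368 and 1.271, two-sided alpha 0.05, n = 120. For a paired t-test with n pairs, power comes from the noncentral t distribution with n − 1 degrees of freedom and noncentrality d√n.

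- d = 0.368, n = 60: 0.368 × √60 = 2.85, power 0.801. This is the smallest n reaching 0.80 and matches the stated 60.
- d = 0.368, n = 120: 0.368 × √120 = 4.03, power 0.979, as stated.
- d = 1.271, n = 8: 1.271 × √8 = 3.59, power 0.867 (stated 0.868). At n = 120 it is 1.000, as stated.
- An independent-groups calculation does not fit: d = 0.368 would need 116 per group, and 60 per group would give power 0.52.

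The stated power therefore belongs to a comparison of two visits with one degree of freedom.

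**Step 2: overall three-visit test at n = 120.** Assumptions: complete data, equal variances and equal correlations between visits (compound symmetry), and the SD of each pairwise change set to 1, so that d stays on the protocol's scale. Since Var(change) = 2σ²(1 − ρ) = 1, σ²(1 − ρ) = 0.5. The repeated-measures F test has 2 and 2(n − 1) = 238 degrees of freedom and noncentrality

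λ = n × Σ(μⱼ − μ̄)² / 0.5.

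For a change at 2 years only, the means are (0, 0, d), the sum of squares is 2d²/3, and λ = 120 × (2d²/3) / 0.5 = 160d². With d = 0.368, λ = 160 × 0.1354 = 21.7. A change of d at both visits gives the same sum of squares. If half the loss recovers by 2 years, the means are (0, d, d/2), the sum of squares is d²/2, and λ = 120d² = 16.3.

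| True change at 1 y, 2 y (d) | λ | Overall F, alpha 0.05 | Overall F, alpha 0.01 | 1-year contrast, alpha 0.05 |
|---|---|---|---|---|
| 0, 0.20 | 6.4 | 0.608 | 0.365 | 0.05 |
| 0, 0.25 | 10.0 | 0.810 | 0.603 | 0.05 |
| 0, 0.30 | 14.4 | 0.932 | 0.809 | 0.05 |
| 0, 0.368 | 21.7 | 0.990 | 0.956 | 0.05 |
| 0.368, 0.368 | 21.7 | 0.990 | 0.956 | 0.979 |
| 0.368, 0.184 | 16.3 | 0.957 | 0.865 | 0.979 |

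**Step 3: simulation, including the fallback.** With 10,000 trials, normal data and correlation 0.5 between visits, no change at 1 year and d = 0.368 at 2 years, the F test is positive in 0.989, the Friedman test in 0.951 and the 1-year paired t-test in 0.050. With d = 0.25 at 2 years only, the figures are 0.811, 0.660 and 0.054. At correlation 0.7 (6,000 trials, d = 0.368 at 2 years only), the results are again about 99%, 95% and 5%.

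**Step 4: power of a named one-year contrast.** At n = 120 and d = 0.368, power is 0.979 at alpha 0.05. If the five-outcome Bonferroni correction applied (0.05 / 5 = 0.01), it would be 0.919. With an assumed 20% loss, 120 × 0.8 = 96 evaluable patients give 0.946 at alpha 0.05. Section 4.4 does not replace patients who discontinue.

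**The case against.** The strongest reply is that the choice of contrast usually belongs in a statistical analysis plan, which is not shown. A mixed model with visit as a factor already estimates the one-year change, and Section 7.2.1 neither says that only an overall F test will be read nor excludes visit contrasts. Its research question also asks how decline changes over time, which a three-visit model answers properly. This stands for the mixed model. It does not rescue the fallback: the protocol fixes the Friedman test, and that test cannot give a one-year answer.

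A reader might infer several stronger points that the protocol does not support:

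- **That a 2-year change would make the primary test positive.** No test is labelled primary, no success rule is stated, and the endpoint is worded as a measurement. The mixed model is only the sole test of change given.
- **That power is lost.** For a sustained d = 0.368 the overall test has power 0.990, against 0.979 for the contrast.
- **That the sample size is wrong.** This calculation needs only 8 to 60 patients. The 120 rests on recruitment and on the prediction-model calculation (90 to 120).
- **That the overall test is faulty because improvement can make it significant.** A two-sided one-year contrast has the same property; in both cases direction is read from the estimates.
- **That the error rate is inflated by choosing among contrasts.** The protocol proposes no such choice.

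The scenario of no change at 1 year and the full effect at 2 years is also an assumption. Nothing in the protocol predicts it, and the table shows how the result varies with the size of the later change. The Friedman figures were simulated on normal data, although the plan reserves that test for non-normal data.

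**Conclusion.** The concern holds as a mismatch between a one-year endpoint and a three-visit test. If the test in Section 7.2.1 is read as an overall test, significance does not show a change at one year. With no 1-year change and a 2-year change of d = 0.20 to 0.368, the F test is positive in 61% to 99% of trials at alpha 0.05, while a one-year contrast stays at 5%. These figures assume 120 patients, complete data and compound symmetry; another covariance pattern would alter their size, not the direction.

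The consequence is limited to interpretation of one of the two primary endpoints. The NTCP endpoint has its own analysis and sample size and is unaffected. Because the study describes itself as exploratory and the same model can give the needed estimate, this is a correction worth making before analysis, not a flaw that undermines the design.

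**What to change.** In Section 7.2.1, for the one-year endpoint:

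- Make the baseline-to-1-year change from the mixed model, with visit as a categorical factor, the main analysis for each outcome, and report it with its confidence interval.
- Replace the Friedman fallback for this endpoint with a paired baseline-to-1-year test, such as the Wilcoxon signed-rank test.
- Report the overall time effect and the baseline-to-2-year change as secondary.
- State whether the five-outcome Bonferroni correction applies to this contrast. Section 7.2.1 currently describes that correction after the predictor models, for the outcomes being predicted, so its application to change over time should not be assumed.

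The cost is wording only: same visits, same data, same mixed model, and no change in sample size. The downside is that a change seen only at 2 years no longer counts towards the one-year endpoint; it would be reported as a secondary result.

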4.4 Subject discontinuation or withdrawal

Participation can be discontinued at any time if the subject, the Investigator, or the Sponsor feels that it is not in the subject's best interest to continue. The following is a list of possible reasons for study treatment discontinuation:

- Screening failure
- Subject withdrawal of consent
- Subject is not compliant with study procedures
- Lost to follow-up
- Sponsor request for early termination of study
- Subject death
- Progressive disease or relapse during follow-up

All subjects are free to withdraw from participation at any time, for any reason, specified or unspecified, and without prejudice. Reasonable attempts will be made by the Investigator to provide a reason for subject withdrawals. The reason for the subject's withdrawal from the study will be specified in the subject's source documents and the Case Report Form (CRF). The Investigator will make every effort to contact subjects who are lost to follow-up. Attempts to contact such subjects must be documented in the subject's records (e.g., times and dates of attempted telephone contact, receipt for sending a registered letter, etc.). Subjects who prematurely discontinue are not to be replaced. For subjects considered lost to follow-up, the CRF must be completed up to the last visit performed.

5. Trial Procedures

Subjects will be screened at the consultation of the neurosurgeon (after biopsy or surgery) or after physician referral to the local radiotherapy-oncology centre. This study will be listed at www.clinicaltrials.gov.

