5.1 By visit

Each patient will have 5 trial visits. The sequence of procedures to be performed at each visit is detailed below.

		SCREENI							END
		NGS PHASE	FOLLO	V-UP	PHASE				OF STUDY
Visit name	Protocol	Screenings visit	Baseline visit*	RT start	End of RT	3 months after	1 year after RT	2 years after RT	End of study visit°
Day				DO	Dstop	3 M	12 M	24M	24 M
Visit window	3.4	D-28 to 0	D -21 to 0		+/- 3D	+/- 2 W	+/- 4 W	+/- 4W	+/- 8W
Informed consent	IC	x							
Eligibility criteria assessment	4	x							
Patient information and history ^a	R	x							
Tumour characteristics ^a	R	x							
RT charachteristics ^a	R				x				
Questionnaires ^b	5.3		x				х	х	
Neurocognitive testing ^c	5.2		x				x	x	
MRI ^d	5.4		x			х	х		
RT plan ^d					x				
CRF toxicity ^a	6.2			x	х				х

End of study	R					х
assessment						

*: minimally 4 weeks after surgery

IC: informed consent form

R: REDCap

o: after 2 years or at progression

a: in REDCap (by CTA or MD)

b: in REDCap (online survey, filled in by patient via REDCap platform)

c: in REDCap (by neuropsychologist)

d: to upload coded DICOM images and RT plan in OncoPlace (by CTA)

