5.2 Neurocognitive assessment

We will perform a standardized neurocognitive test battery in all patients at baseline (prior to RT) and each consecutive year (1 year and 2 years post-RT). The acquisition of neurocognitive assessments takes approximately 1 hour. Results will be followed over time and compared to normative data ^{21,22}.

All these tests and questionnaires have been extensively described and used to quantify neurocognitive functioning in adults. Both neurocognitive testing and completion of the questionnaires takes place in the hospital.

We will use a broad evaluation of neurocognitive performance.

- The Montreal Cognitive Assessment (MOCA), is a screening instrument for cognitive deficits in multiple domains²³.
- Trail Making Task (TMT)²⁴, is an executive task which requires to link characters and digits in the correct sequence.
- Digit span (subtest of the Wechsler Adult Intelligence Scale(WAIS))²⁵ is a working memory task, which requires to repeat digits in same, reversed and sequencing order.
- The Hopkins Verbal Learning Test- Revised (HVLT-R)²⁶ is a verbal memory task for which participants need to repeat 12 words (three repetitions of free-recall) to assess verbal learning. Afterwards, they are asked to repeat or recognize the memorized words (Delayed recall and recognition).
- Controlled Word Association Test (COWAT)²⁷ assesses categoric and phonemic fluency. The participant is required to make verbal associations to a category or different letters of the alphabet by saying all the words which they can think of in this category or beginning with a given letter.
- The Stroop Color and Word Test (SCWT)²⁸ assesses the ability to inhibit cognitive interference that occurs when the processing of a specific stimulus feature impedes the simultaneous processing of a second stimulus attribute.
- The digit symbol substitution test of the WAIS (coding)²⁹ measures processing speed. This test consists of digit-symbol pairs followed by a list of digits. Under each digit the subject

should write down the corresponding symbol as fast as possible. The number of correct symbols within the allowed time is measured.

Cognitive domain	Neurocognitive test	Outcome measurement time				
Attention	TMT B					
Memory	HVLT immediate recall	Sum score - learning				
	HVLT delayed recall	Sum score				
	HVLT recognition	Good recognition-mistakes				
	WAIS IV digit span forward	Total number of series				
Executive functioning	COWAT	Sum of words				

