7.2 Analysis

Analyses and statistical methods will be applied to all subjects.

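### If scores are judged non-normal, the Friedman fallback drops patients with a 1-year score but no 2-year test, and it gives no estimate of decline

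*Protocol*

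**What the plan says.** The main longitudinal analysis is in protocol section 7.2.1: "We will assess the evolution in the z-scores with a mixed repeated measures model to test changes throughout time". The next sentence sets the alternative: "However, if the data are not normally distributed, the Friedman test will be used as alternative approach". It names no normality test or threshold, and does not say whether the scores or the model residuals are meant.

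The same section states: "The performance on neurocognitive measures of the patients will be assessed at 3 timepoints over time". Section 5.2 places these before radiotherapy and at 1 and 2 years after it. Section 3.2 lists the prevalence and severity of decline from baseline at one year as a primary endpoint, and the first research question in 7.2.1 asks how severe the decline is.

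On missing visits, section 4.4 gives "Progressive disease or relapse during follow-up" among the possible reasons for discontinuation and adds: "Subjects who prematurely discontinue are not to be replaced". The schedule in section 5.1 places the end-of-study visit "after 2 years or at progression" and marks no neurocognitive testing at that visit. Section 7.2 says: "Analyses and statistical methods will be applied to all subjects". No dropout rate is given, and nothing says how the Friedman test would handle a missed visit.

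**The concern.** The Friedman test ranks each patient's scores across visits, so it can use only patients with every visit. A likelihood-based mixed model has no such restriction. The switch therefore changes the patients analysed as well as the method. Those it loses include patients whose 1-year endpoint was fully observed but who stopped before the 2-year test. Because the study ends at progression, some of these losses will be tied to the course of disease.

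The switch also changes what is learned. The Friedman test asks whether the three visits differ anywhere in rank. It gives no size of decline and does not separate baseline-to-1-year from the later interval, which is the contrast the primary endpoint needs.

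Finally, each cognitive test could be switched or not according to an unspecified check of the data. Two tests within one cognitive domain could then be reported by different methods on different patients.

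**Working it through.** **1. The plan's own figures.** Section 7.1 gives d = 0.368 and d = 1.271, two-sided alpha 0.05, required samples of 60 and 8, and power 0.979 and 1.000 with 120 patients. A paired t test (noncentrality d x sqrt(n), n - 1 degrees of freedom) reproduces them:
- d = 0.368: power 0.801 at n = 60. At n = 120 the noncentrality is 0.368 x sqrt(120) = 4.03 and power is 0.979.
- d = 1.271: power 0.867 at n = 8 (the plan prints 0.868) and 1.000 at n = 120.

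The calculation at n = 120 assumes 120 complete baseline and 12-month pairs, with no allowance for loss.

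**2. Who enters each analysis.**

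| Tests available | Mixed model | Friedman test |
|---|---|---|
| Baseline, 1 year, 2 years | used | used |
| Baseline, 1 year | used, including the 1-year change | dropped |
| Baseline, 2 years | used | dropped |
| Baseline only | baseline score only, no change observed | dropped |

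The second row matters most and needs no assumed number.

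**3. Counts.** Assume a fraction q1 = 0.10 lost before year 1 and q2 = 0.20 lost between years 1 and 2. Patients with 1-year data: 120 x 0.90 = 108. Complete on all three visits: 120 x 0.70 = 84. The fallback then discards 108 - 84 = 24 patients with an observed 1-year change.

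**4. Fewer patients, no selection.** Paired-t power at d = 0.368 is 0.966, 0.946, 0.915 and 0.869 with 108, 96, 84 and 72 patients, against 0.979 with 120. This is a yardstick for lost numbers only, not the power of the Friedman test. The loss is modest.

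**5. Selection.** The protocol gives d but no SD-scale change. Assuming SD 1 and a between-visit correlation of 0.7, the SD of change is sqrt(2 x (1 - 0.7)) = 0.775, and 0.368 x 0.775 = 0.285, so the true 12-month change is set at -0.285 SD. Let e be the extra decline in those lost by 2 years, f = q1 + q2, and baseline be unrelated to later loss. Then:
- mean change in completers = -0.285 + e x f
- expected mixed-model 1-year change = -0.285 + e x (f - q2/(1 - q1))

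For q1 = 0.10 and q2 = 0.20, f = 0.30 and f - q2/(1 - q1) = 0.30 - 0.222 = 0.078:
- e = 0.3: completers -0.285 + 0.090 = -0.195; mixed model -0.285 + 0.023 = -0.262
- e = 0.5: completers -0.285 + 0.150 = -0.135; mixed model -0.285 + 0.039 = -0.246

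A simulation (1,500 runs per scenario, 120 patients, three visits) agrees to within about 0.002. Its results over a range of assumed losses, as completers / mixed model:

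| Lost before year 1, then years 1-2 | Complete | With 1-year data | e = 0 | e = 0.3 | e = 0.5 |
|---|---|---|---|---|---|
| 5%, 5% | 108 | 114 | -0.285 / -0.285 | -0.257 / -0.272 | -0.236 / -0.263 |
| 10%, 10% | 96 | 108 | -0.283 / -0.284 | -0.223 / -0.257 | -0.183 / -0.241 |
| 10%, 20% | 84 | 108 | -0.287 / -0.286 | -0.194 / -0.261 | -0.135 / -0.244 |
| 20%, 20% | 72 | 96 | -0.287 / -0.286 | -0.164 / -0.239 | -0.086 / -0.209 |

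The completers' means describe the patients on whom the Friedman test would rest. The test itself would not report them. The fallback's own effect is the gap between the two figures: in the 10%, 20% row, 0.261 - 0.194 = 0.067 SD and 0.244 - 0.135 = 0.109 SD.

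**The case against.** The best reply is that the reach is narrow. Impairment frequencies, the linear models at each timepoint, the dosimetry regressions and the NTCP models do not pass through the Friedman test. That stands.

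Several stronger readings are tempting, and the documents do not support them:

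- *The fallback biases the estimate of severity.* It produces no estimate to bias. The fair statement is that the test rests on a selected group and the severity question goes unanswered.
- *The fallback will be used often.* Timed and bounded scores may be skewed, but the analysed values are z-scores from norms, and nothing in the protocol shows how they will be distributed.
- *A rank test wastes power here.* The usual unfavourable efficiency figure assumes normal data, which is when the fallback is not used. Step 4 shows that losing patients alone costs little.
- *Losing covariates is a further harm.* Section 7.2.1 names none for the mixed model; its covariates belong to the separate linear models.
- *It flatly contradicts the sentence in section 7.2 about all subjects.* That sentence is generic, and no analysis meets it for patients without data. The tension is real only for patients whose observed 1-year scores are thrown away.

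It is also fair that the mixed model is no cure. A patient lost before year 1 has no observed change under either method, and the mixed model is itself biased when loss depends on unseen decline. In every scenario with extra decline it was nearer the truth than the completers were. With no extra decline, both were unbiased.

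An analysis plan could define the normality check. That would settle the trigger, but not the loss of patients or the missing estimate once the switch is made.

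**Conclusion.** The point holds in a conditional form and should be corrected. The protocol expressly replaces a method that can use partial follow-up and estimate the 1-year change with one that can do neither. This follows from the nature of the two methods and the visit schedule, without any assumed figure. It takes effect only if the switch is triggered, and only in the change-over-time analysis.

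The size is illustrative. The loss rates, the extra decline in those lost and the correlation of 0.7 are all assumptions. Under 10% and 20% loss with 0.3 to 0.5 SD extra decline, the completers' change falls short of the truth by 0.09 to 0.15 SD, or 0.09/0.285 = 32% to 0.15/0.285 = 53%. The mixed model falls short by about 0.02 to 0.04 SD. If those lost decline no more than the rest, there is no distortion. What remains then is a modest loss of numbers and the absence of an estimate.

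The comparison reads the protocol's mixed model as likelihood-based and fitted to all available visits. The protocol does not spell this out, so the fix should.

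**What to change.** In section 7.2.1, delete the Friedman test as the replacement analysis and state instead:

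- The mixed model is fitted to all available visits for every cognitive test, and the baseline-to-1-year contrast is reported with its confidence interval.
- Normality is judged on the model residuals.
- Where residuals are clearly non-normal, robust or bootstrap standard errors are used, or timed raw scores are transformed before conversion to z-scores. A log cannot be applied directly to z-scores, which may be negative.
- A Friedman test may be kept at most as a sensitivity analysis, labelled as restricted to patients with all three visits.

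This replaces one sentence, needs no new data, and costs only slightly more analysis work.

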3.4 Trial Design

This is an observational cohort study which evaluates primary brain tumour patients longitudinally at the following timepoints: baseline (minimal 4 weeks after surgery (if indicated), before radiotherapy), three months (+/- 2 weeks) after end of radiotherapy, 1 year after end of radiotherapy (+/- 1 month) and 2 years after end of radiotherapy (+/- 1 month). At each visit, neurocognitive testing, a self-report inventory and/or advanced MR imaging will take place. During and after radiotherapy and at each follow-up visit, adverse events will be monitored using CTCAEv5.0²⁰.

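### The dose models in 7.2.1 are set to run at every test visit, including the pre-radiotherapy baseline, where a dose coefficient cannot be an effect of radiation

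*Protocol*

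**What the plan says.** Protocol 7.2.1 sets the number of test visits: "The performance on neurocognitive measures of the patients will be assessed at 3 timepoints over time". Section 5.2 names them, with the battery given "in all patients at baseline (prior to RT) and each consecutive year (1 year and 2 years post-RT". The schedule in 5.1 agrees: neurocognitive testing and questionnaires are marked at baseline, 1 year and 2 years, and the 3-month visit carries MRI only. Section 3.4 fixes the first visit as "baseline (minimal 4 weeks after surgery (if indicated), before radiotherapy".

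Section 7.2.1 then states the purpose of the models: "The effects of the patient- and treatment-related predictors on the neuropsychological and questionnaire scores will be investigated using general linear models". Their content and scope follow: "predictors= tumour location, radiation dose, covariates= gender, age at treatment, time since treatment and socio-economic status) at each timepoint". It adds: "Effect sizes of the tests will be reported". No sentence exempts the baseline visit, and none describes a baseline fit as a check for confounding. The same section plans a mixed repeated measures model for change over time, but gives it no dose term.

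**The concern.** Read literally, the rule calls for a model of pre-radiotherapy scores on radiation dose. Two of its terms have no proper value at that visit. Delivered dose is zero for everyone, so the only dose that varies between patients is the one planned for later. Time since radiotherapy is undefined.

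A plan-dose coefficient at baseline can show only that patients destined for higher doses already scored differently, or that chance made it look so. This matters for the secondary endpoint in 3.3 that links cognition to dosimetry, and for the objective in 3.1 about dose-dependence after radiotherapy. A baseline association, if present, is a warning against reading the 1- and 2-year coefficients causally. The plan does not say that it should be read that way.

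**Working it through.** **1. Setting the sections side by side**

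| Item | Source | Value at the baseline visit |
|---|---|---|
| Visits modelled | 7.2.1 | all three; no exception |
| First visit | 5.2, 5.1, 3.4 | before radiotherapy |
| Delivered dose | follows from 3.4 | 0 for every patient |
| Time since radiotherapy | follows from 3.4 | none |
| Time since surgery, if treatment is read to include it | 3.4: surgery only where indicated | none for unoperated patients |

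The model as written therefore cannot be fitted at baseline to all patients under either reading of treatment. Confounding is plausible from the protocol itself: 3.2 lists tumour size as an explanatory variable, but the 7.2.1 model does not contain it.

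**2. The plan's own figures**

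Section 7.1 gives no figure for the dose models. Its power statement concerns a paired change and is reproduced by a two-sided paired t-test at 0.05 with noncentrality d√n:

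- d = 0.368, n = 60: 0.368 × 7.746 = 2.85, power 0.801 (stated 0.800). At n = 120 the power is 0.979 (stated 0.979).
- d = 1.271, n = 8: 1.271 × 2.828 = 3.59, power 0.867 (stated 0.868). At n = 120 the noncentrality is 1.271 × 10.954 = 13.9, so power is 1.000 as stated.

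The point raised here changes none of these. The Bonferroni divisor is the 5 outcomes, 0.05/5 = 0.01, and is not multiplied by visits. Removing the baseline fits leaves that threshold where it is.

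**3. Illustration under assumptions that the protocol does not supply**

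Assume n = 120 and a true dose effect of zero. An unmeasured severity factor correlates r with planned dose and −c with underlying cognition, equally at baseline and follow-up. The test error variance is 0.25 on a true variance of 1, so reliability is 1/1.25 = 0.8. The covariates are age, sex, location and socio-economic status. Time since treatment is left out because it has no baseline value. There were 2,000 simulated trials per row. Entries are the share of trials with a dose term at p < 0.05.

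| r, c | Baseline model | Follow-up, no baseline score | Follow-up, baseline score added | Change from baseline |
|---|---|---|---|---|
| 0, 0 | 5.8% | 5.6% | 5.2% | 5.4% |
| 0.3, 0.3 | 12.4% | 11.8% | 5.8% | 5.1% |
| 0.5, 0.3 | 31.4% | 29.2% | 7.5% | 4.8% |
| 0.5, 0.5 | 68.6% | 66.3% | 12.7% | 5.1% |
| 0.6, 0.5 | 83.8% | 82.8% | 16.5% | 4.8% |

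At the 0.01 level the four confounded baseline rates are 3.2%, 13.2%, 43.3% and 63.8%.

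Hand check of the 0.5, 0.5 row: the expected coefficient is −rc = −0.25 (simulated −0.249). The correlation is 0.25/√1.25 = 0.224. With 114 degrees of freedom, t ≈ 0.224 × √114 / √(1 − 0.05) = 2.45. Against a critical value of 1.98 the rejection rate is Φ(0.47) ≈ 0.68.

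The expected coefficient is −rc at follow-up too, so dropping the baseline fit does not by itself reduce confounding. With the baseline score added, the coefficient in this row becomes (−0.25 × 1.25 + 0.25) / (1.25 − 0.0625) = −0.053. That is much smaller but not zero, because the baseline score carries measurement error.

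**The case against.** The strongest reply is that the authors meant post-radiotherapy visits only. Time since treatment makes no sense before treatment, and the question in 7.2.1 concerns decline after it. That is a fair guess at intent, and the fault may be no more than loose wording. The text still defines three visits, one of them pre-radiotherapy, and applies the models to each.

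Treatment could also mean the multimodal treatment described in 3.1, which would give operated patients a value at baseline. This stands for them, but not for unoperated patients, and it does not touch the dose term.

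Three stronger readings should be resisted:

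- A reader might infer that confounding will be reported as a radiation effect. The protocol does not say so. Its talk of effects is ordinary regression language that also covers age, gender and location, which are legitimate at baseline. Nor does it say which dose value would be entered there.
- A reader might count 5 of 15 dose tests (5 domains at 3 visits) as wasted. That counts only the 7.2.1 domain models. Dose is also tested in 7.2.2, 7.2.3 and 7.2.4.
- A reader might take the simulated rates as the trial's error rate. They rest wholly on assumed correlations and on a model without time since treatment, which is not quite the one specified.

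It is also right that deleting the baseline fit would remove the one result able to reveal confounding, while leaving the follow-up models as they are. The fix has to allow for that.

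**Conclusion.** The point holds as a fault in the stated scope of the 7.2.1 models. At baseline they include a dose that has not been given and a time that has no value relative to radiotherapy. A plan-dose coefficient there can reflect only confounding or chance, and the text does not separate it from the post-treatment effects.

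This conclusion rests on the visit definitions alone and needs no assumption about how strong the confounding is. The frequency of a significant baseline coefficient cannot be derived from the protocol. It is 5% without confounding, and the 12% to 84% in the illustration applies only under the correlations assumed there. The affected analysis serves a secondary endpoint of a study that calls itself exploratory. The sample size, the 0.01 threshold and the NTCP models in 7.2.4 are unaffected. It should be corrected, but it does not threaten the main objective.

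**What to change.** In 7.2.1, for every model containing radiation dose or time since treatment, replace the closing words of the parenthesis on timepoints with *at 1 year and at 2 years after radiotherapy*.

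In the same sentence, add the baseline z-score of the outcome concerned as a covariate, or use a dose-by-time term in the mixed model already planned. This second step is needed because limiting the visits leaves the follow-up dose coefficients confounded. Neither option removes a factor that drives both dose and later change in cognition.

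If a baseline model with plan dose is kept, fit it without time since treatment and report it only as a negative-control check for confounding, not as an effect of dose.

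The baseline scores are already collected, so no new data are required. The cost is the wording, one extra covariate per model and a little more analysis work.
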